
Conditions to be fulfilled for asciminib switch
	
1. Failure to bosutinib treatment up to 96 weeks after the last patient received the first dose (adapted from the 2013 ELN Guidelines; Baccarani et al 2013). Patients must meet at least 1 of the following criteria. Failure is defined as follows:
 
 • Three months after the initiation of therapy or thereafter: No CHR or > 95% Ph+ metaphases. • Six months after the initiation of therapy or thereafter: BCR-ABL1 ratio > 10% IS and/or > 65% Ph+ metaphases. • Twelve months after initiation of therapy or thereafter: BCR-ABL1 ratio > 10% IS and/or > 35% Ph+ metaphases. • At any time after the initiation of therapy, loss of CHR, CCyR or PCyR. • At any time after the initiation of therapy, detection of new BCR-ABL1 mutations which potentially cause resistance to study treatment (asciminib or bosutinib). • At any time after the initiation of therapy, confirmed loss of MMR in 2 consecutive tests. • At any time after the initiation of therapy, new clonal chromosome abnormalities in Ph+ cells: CCA/Ph+. 
Conditions preventing patients to switch to asciminib:
 
 • Any Grade 3 or 4 toxicity which has not resolved to Grade 2 or lower within 28 days and before starting asciminib treatment. • Asymptomatic (Grade 2) pancreatitis if not resolved within 28 days • Disease progression while on bosutinib treatment. The following events are considered disease progression: 
 • Accelerated phase (AP) as defined by any of the following: 
 • ≥ 15% blasts in the peripheral blood or bone marrow aspirate, but < 30% blasts in both the peripheral blood and bone marrow aspirate. • ≥ 30% blasts plus promyelocytes in peripheral blood or bone marrow aspirate. • ≥ 20% basophils in the peripheral blood. • Thrombocytopenia (< 100 x 10⁹/L) that is unrelated to therapy. • Blast crisis (BC) as defined by any of the following: 
 • ≥ 30% blasts in peripheral blood or bone marrow aspirate

	
 • Appearance of extramedullary involvement other than hepatosplenomegaly proven by biopsy (i.e., chloroma). • QTcF at time of switch > 480 msec or inability to determine QTc interval
Investigational and reference therapy	Asciminib 40 mg BID Bosutinib 500 mg QD

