1.2 Introduction to investigational treatment

1.2.1 Overview of asciminib (ABL001)

[figure not shown]
Asciminib is an orally bioavailable specific BCR-ABL1 inhibitor with a novel mechanism of action. In contrast to inhibitors such as imatinib, nilotinib, dasatinib and bosutinib that bind within the ATP-binding site of the ABL kinase domain, asciminib inhibits ABL tyrosine kinase activity by binding to a particular allosteric site on the kinase domain, which has only been identified on ABL1, ABL2 and BCR-ABL1. Consequently, asciminib is specific for the latter three enzymes.

Asciminib potently and selectively inhibits the proliferation of cell lines that express BCR-ABL1. By virtue of asciminib not interacting with the ATP-binding site, the drug maintains activity against cells expressing clinically observed ATP-binding TKI resistance mutations.

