1.2.1.2 Clinical experience

Asciminib is undergoing evaluation in a first-in-human (FIH) phase I clinical study, study [CABL001X2101].

This study evaluates patients with 1) CML who have been treated with at least 2 prior TKIs, or 2) who have the T315I mutation and have been treated with at least 1 prior TKI, or 3) who have Acute Lymphoblastic Leukemia (ALL) and have been treated with at least 1 prior TKI. The study evaluates administration of asciminib in a BID single agent dosing schedule, as well as in a QD single agent schedule, and in combination with nilotinib, imatinib, and dasatinib. In the present document, discussion will focus on data from CML patients treated with asciminib BID single agent only.

As of 01-Sep-2017, a total of 239 CML or Ph+ ALL patients have been treated with either single agent oral asciminib or in combination cohorts. 150 CML patients have been treated with asciminib monotherapy. Based on the preliminary efficacy, safety and tolerability in patients with CML-CP or CML-AP treated with asciminib as a single agent on a BID schedule in study [CABL001X2101] and the results of a population PK/PD exposure-response model, the

dose of 40 mg BID has been selected as the recommended dose to be used in future studies in patients with CML-CP who do not harbor T315I mutations.

Efficacy:

Preliminary data from the ongoing Phase I FIH study [CABL001X2101] indicate that asciminib exhibits single-agent activity in patients with CML who have failed at least two prior TKIs or are intolerant to TKIs, as demonstrated by major molecular response and reduction in the BCR-ABL1 % IS. Asciminib has demonstrated anti-tumor activity at doses greater or equal to 10 mg BID as well as daily higher doses.

To date, efficacy data in 141 patients with chronic-phase CML treated with single agent asciminib therapy (10-200 mg BID and 80-200 mg QD) are available (113 patients without T315I mutation and 28 with T315I mutation).

Of the 62 patients with BCR-ABL1 no greater than 10 % IS at screening and without T315I mutation, 1-log reduction of BCRABL1 % IS was achieved in 16 of 62 (25.8%) patients by 6 months and 19 of 62 (30.6%) patients by 12 months. For asciminib 40 mg BID dose, of the 17 patients studied, 1-log reduction of BCRABL1 % IS was achieved in 5 of 17 (29.4%) patients by 6 months, and 12 months.

Please refer to the latest [Asciminib Investigator's Brochure] for more details.

Safety:

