The study design incorporates a 2:1 randomization, allocating more patients to the asciminib arm in order to learn more about the safety profile of the experimental therapy, whereas the safety of bosutinib therapy is well documented.

Patients randomized to the bosutinib arm who have documented treatment failure as defined by the 2013 ELN Guidelines at any time point will have the option to receive asciminib at the investigator's discretion and if it is in the patient's best interest. The purpose of the option to switch to asciminib is to provide this investigational treatment option to eligible patients who will have limited available therapeutic options outside of the study.

[figure not shown]
[figure not shown]
Treatment duration for each patient in the present study is up to 96 weeks after the last patient received the first dose in the study (which should be an adequate timeframe to address both the primary objective of the study, i.e. determination of the MMR rate at 24 weeks, as well as the secondary efficacy and safety objectives) or up to 48 weeks after the last bosutinib failure patient has switched to asciminib during the treatment period, whichever is longer unless the patient discontinues treatment earlier. Blood samples will be taken in this study from all patients randomized to asciminib in order to describe the pharmacokinetics and possibly identify the sources of variabilities. Exploratory analysis may be performed to establish the relationship between exposure and efficacy or safety.

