A preliminary population PK-PD model has been developed using data from the [CABL001X2101] study (cut-off 2 May 2016). The time course of molecular response (change in BCR-ABL1 ratio % IS levels from baseline) was described using a semi-physiological model accounting for cell maturation, disease progression and existing resistance. Simulations performed (with 100 patients) using asciminib population PK-PD model revealed that at a dose of 40 mg BID, ~41% (CI₉₅%; 31-51%) of chronic phase CML patients having failed ≥ 2 TKI or intolerant to TKIs are likely to exhibit a 1 log₁₀ reduction of (%) BCR-ABL1 mRNA transcript levels from baseline at 6 months, and 53% (CI₉₅%; 43-63%) at 12 months, and predicting higher probability of achieving BCR-ABL1 mRNA ≥ 1 log reduction at 6 and 12 months with 40 mg BID versus 20 mg BID.

Additional preliminary PK-efficacy and PK-safety analyses to assess the exposure-response relationship for asciminib were conducted ([Section 1.2.1.2](#)). The efficacy measure used was Molecular Response (MR) which is defined as a decline in BCR-ABL1 transcript levels in clinical blood samples of patients with Chronic Myeloid Leukemia (CML). MR was evaluated as both a continuous variable (BCR-ABL1 transcript levels) and categorical variable (whether or not adequate decline in BCR-ABL1 was achieved). The safety measures used were occurrence of Common Toxicity Criteria (CTC) grade 2, 3 or 4 laboratory values for lipase and amylase.

Reviewing the totality of the efficacy, safety, and pharmacokinetic data derived from the [\[CABL001X2101\]](#) study, the recommended dose for asciminib in this phase 3 study is 40 mg BID. Of note, the dose of asciminib single agent BID is further being evaluated in patients with the T315I mutation. At present the recommended dose of 40 mg BID is for patients without the T315I mutation. For this reason, patients with the T315I mutation are excluded from this study.

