2.5 Rationale for choice of comparators drug bosutinib

The guidance provided by the NCCN and the ELN ([Baccarani et al 2013](#)), recommends bosutinib as a treatment in CML-CP patients who fail first-line or second-line treatment with imatinib or nilotinib or dasatinib. Consistent with these recommendations and clinical practice, bosutinib was selected to be an appropriate comparator in a study of 3rd line CML-CP patients after failure of at least 2 prior TKIs, and is the comparator that will be used in the present study.

It is to be noted that bosutinib has no activity against the T315I and V299L mutant form of BCR-ABL1. Patients who have the T315I or V299L mutations documented in their medical record will already be excluded from this study. Bosutinib is known to be active against E255K/V, F317L/V/I/C, F359V/C/I, T315A, and Y253H and therefore, these mutations are not considered in the exclusion criteria for the current study.

Ponatinib is not selected as the comparator in the present clinical trial, because the comparator in this study needs to be an approved agent administered at the approved dose. Currently, the ponatinib dose is being evaluated in a randomized trial as a post-approval commitment due to the occurrence of vascular risks at the current approved dose of ponatinib. The dose of ponatinib that will be approved and will be used in practice at the completion of the present study may not be the approved dose at the time of initiation of the present study.

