5.2 Inclusion criteria

Patients eligible for inclusion in this study have to meet **all** of the following criteria:

1. Male or female patients with a diagnosis of CML-CP \geq 18 years of age

2. Patients must meet all of the following laboratory values at the screening visit:
 - < 15% blasts in peripheral blood and bone marrow
 - < 30% blasts plus promyelocytes in peripheral blood and bone marrow
 - < 20% basophils in the peripheral blood
 - $\geq 50 \times 10^9/L$ ($\geq 50,000/mm^3$) platelets
 - Transient prior therapy related thrombocytopenia ($< 50,000/mm^3$ for ≤ 30 days prior to screening) is acceptable
 - No evidence of extramedullary leukemic involvement, with the exception of hepatosplenomegaly
- 3a. BCR-ABL1 ratio $> 0.1\%$ IS according to central laboratory at the screening examination, for patients intolerant to the most recent TKI therapy
4. Prior treatment with a minimum of 2 prior ATP-binding site TKIs (i.e. imatinib, nilotinib, dasatinib, radotinib or ponatinib)
5. Failure (adapted from the 2013 ELN Guidelines; [Baccarani et al 2013](#)) or intolerance to the most recent TKI therapy at the time of screening
 - Failure is defined for CML-CP patients (CP at the time of initiation of last therapy) as follows. Patients must meet at least 1 of the following criteria.
 - Three months after the initiation of therapy: No CHR or $> 95\%$ Ph+ metaphases
 - Six months after the initiation of therapy: BCR-ABL1 ratio $> 10\%$ IS and/or $> 65\%$ Ph+ metaphases
 - Twelve months after initiation of therapy: BCR-ABL1 ratio $> 10\%$ IS and/or $> 35\%$ Ph+ metaphases
 - At any time after the initiation of therapy, loss of CHR, CCyR or PCyR
 - At any time after the initiation of therapy, the development of new BCR-ABL1 mutations which potentially cause resistance to current treatment
 - At any time after the initiation of therapy, confirmed loss of MMR in 2 consecutive tests, of which one must have a BCR-ABL1 ratio $\geq 1\%$ IS
 - At any time after the initiation of therapy, new clonal chromosome abnormalities in Ph+ cells: CCA/Ph+
 - Intolerance is defined as:
 - Non-hematologic intolerance: Patients with grade 3 or 4 toxicity while on therapy, or with persistent grade 2 toxicity, unresponsive to optimal management, including dose adjustments (unless dose reduction is not considered in the best interest of the patient if response is already suboptimal)

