5.3 Exclusion criteria

Patients eligible for this study must not meet **any** of the following criteria:

1. Known presence of the T315I or V299L mutation at any time prior to study entry
2. Known second chronic phase of CML after previous progression to AP/BC
3. Previous treatment with a hematopoietic stem-cell transplantation
4. Patient planning to undergo allogeneic hematopoietic stem cell transplantation
5. Cardiac or cardiac repolarization abnormality, including any of the following:
 - History within 6 months prior to starting study treatment of myocardial infarction (MI), angina pectoris, coronary artery bypass graft (CABG)
 - Clinically significant cardiac arrhythmias (e.g., ventricular tachycardia), complete left bundle branch block, high-grade AV block (e.g., bifascicular block, Mobitz type II and third degree AV block)
 - QTcF at screening $\geq 450 \text{ msec}$ (male patients), $\geq 460 \text{ msec}$ (female patients)
 - Long QT syndrome, family history of idiopathic sudden death or congenital long QT syndrome, or any of the following:

- Risk factors for Torsades de Pointes (TdP) including uncorrected hypokalemia or hypomagnesemia, history of cardiac failure, or history of clinically significant/symptomatic bradycardia
 - Concomitant medication(s) with a “Known risk of Torsades de Pointes” per www.crediblemeds.org/ that cannot be discontinued or replaced 7 days prior to starting study drug by safe alternative medication.
 - Inability to determine the QTcF interval
6. Severe and/or uncontrolled concurrent medical disease that in the opinion of the investigator could cause unacceptable safety risks or compromise compliance with the protocol (e.g. uncontrolled diabetes, active or uncontrolled infection, pulmonary hypertension)
 7. History of acute pancreatitis within 1 year of study entry or past medical history of chronic pancreatitis
 9. History of acute or chronic liver disease
 10. Known presence of significant congenital or acquired bleeding disorder unrelated to cancer
 11. History of other active malignancy within 3 years prior to study entry with the exception of previous or concomitant basal cell skin cancer and previous carcinoma in situ treated curatively
 12. Known history of Human Immunodeficiency Virus (HIV), chronic Hepatitis B (HBV), or chronic Hepatitis C (HCV) infection. Testing for Hepatitis B surface antigen (HBs Ag) and Hepatitis B core antibody (HBcAb / anti HBc) will be performed at screening

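### The Amendment 3 protocol summary lets a new T315I or asciminib-resistance mutation qualify a bosutinib patient for asciminib 40 mg BID, against the protocol's own dose statement

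*Combined protocol and SAP*

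**What the plan says.** The switch conditions are in the Amendment 3 protocol summary, under the conditions to be fulfilled for asciminib switch. At least one of seven bosutinib-failure criteria must be met. The fifth is "detection of new BCR-ABL1 mutations which potentially cause resistance to study treatment (asciminib or bosutinib". Four conditions prevent the switch: unresolved grade 3 or 4 toxicity, unresolved grade 2 pancreatitis, progression to accelerated phase or blast crisis, and a long or undeterminable QTc.

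Other parts of the Amendment 3 protocol bear on this:

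- Section 1.2.1.2 calls 40 mg BID the "recommended dose to be used in future studies in patients with CML-CP who do not harbor T315I mutations".
- Section 2.3 repeats it: "At present the recommended dose of 40 mg BID is for patients without the T315I mutation". It gives this as the reason for keeping T315I patients out of the study and says dosing for T315I is still under evaluation.
- Section 5.3, exclusion criterion 1, covers "Known presence of the T315I or V299L mutation at any time prior to study entry".
- Section 2.5 states that "bosutinib has no activity against the T315I and V299L mutant form of BCR-ABL1".
- Section 5.2, the parallel failure criterion for study entry, refers to "the development of new BCR-ABL1 mutations which potentially cause resistance to current treatment".
- Section 6.2 does not allow asciminib above 40 mg BID.
- The Amendment 2 change log says Section 7.1.6 was revised so that T315I or V299L found at any time is among the cases where treatment must be discontinued. Section 4.1.1 applies Section 7.1.6 to stopping asciminib after a switch.

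**The concern.** A switch rule should send patients to a drug and dose that the protocol regards as suitable for them. Here the qualifying mutation may be one that undermines the new drug, or one for which the only permitted full dose is not the recommended dose. The entry exclusion does not help, because it looks back only to the time before study entry, while the switch concerns mutations that emerge on bosutinib.

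What is at stake is patient management and the clarity of the switched cohort. These patients will have failed at least a third TKI, and Section 2.6 describes patients after two failures as already at increased risk of progression. Table 3-1 makes the safety of asciminib after bosutinib failure a secondary objective and its efficacy in that setting an exploratory one.

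**Working it through.** No sample-size, power or alpha figure is involved, so the check sets the texts side by side.

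**Counting the rules in the summary.** The qualifying criteria are the 3-month, 6-month and 12-month milestones, loss of CHR/CCyR/PCyR, a new mutation, confirmed loss of MMR, and new clonal abnormalities in Ph+ cells: 7 in all, of which 1 concerns a mutation. The preventing conditions are toxicity, pancreatitis, progression and QTcF: 4 in all, of which 0 concern a mutation.

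**Tracing three cases of a new mutation on bosutinib.**

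| Mutation | Meets the switch criterion? | Named as preventing it? | Dose statement (1.2.1.2, 2.3) | Section 7.1.6 as logged |
|---|---|---|---|---|
| T315I | Yes; bosutinib is inactive against it (2.5) | No | 40 mg BID not the recommended dose | Must discontinue |
| V299L | Yes; bosutinib is inactive against it (2.5) | No | No restriction stated | Must discontinue |
| Asciminib-resistance mutation | Yes, by the parenthesis | No | No statement | Not named |

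The third category is not empty. Section 1.2.1.1 names A337V as the mutation seen with asciminib in the xenograft model.

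For T315I the dose statement and the logged stopping rule both point away from asciminib, while the switch criterion points towards it. For V299L only the logged rule conflicts with the switch. That is why V299L needs an explicit decision and not an automatic bar.

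**Size.** Planned bosutinib patients: 222 × 1/3 = 74 (Section 5.1, 2:1 allocation). This is a ceiling on everyone who could switch for any reason. The Amendment 3 rationale counts four patients who could have used the option by 15-Oct-2018. No rate of T315I emerging on bosutinib and no switch rate is given, so no expected number can be calculated.

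**Effect on the main analyses.** The Amendment 3 rationale treats any patient meeting the failure criteria as a non-responder for that time point and all later ones, in either arm and regardless of any switch. Post-switch efficacy is analysed separately. MMR at weeks 24 and 96 is therefore untouched.

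**The case against.** The strongest reply is that the summary is not the operative text. Section 4.1.1 sends the reader to Section 7.1 for switch eligibility, and the Amendment 3 log says a new Section 7.1.2.2 holds it. The text available for this review stops inside Section 7.1.2. Summary and body do differ elsewhere: the summary's entry criterion speaks of resistance to study treatment where Section 5.2 speaks of current treatment, and the summary's purpose keeps a 1% threshold that Section 2.1 dropped. This stands, and it confines the finding to the summary.

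Second, the logged Section 7.1.6 rule, read together with the switch conditions, takes a T315I patient off study treatment. The itemised Amendment 3 edits to that section do not mention removing it. This limits exposure. But it is a rule for stopping; on bosutinib it applies at the very moment the switch opens, and the summary does not say that it closes the switch.

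Third, the governing phrase is failure of bosutinib, and the parenthesis may merely expand the term study treatment. That is plausible as intent, but the wording still admits asciminib resistance.

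Fourth, although failing patients "at any time point will have the option to receive asciminib", Section 2.2 leaves this to the investigator and the patient's best interest, and Table 7-2 records mutation status at switch screening. Both are real safeguards. Neither tells the site what a T315I result means.

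A reader might also infer that asciminib does not work against T315I. The documents do not support this. Section 1.2.1 says "the drug maintains activity against cells expressing clinically observed ATP-binding TKI resistance mutations", and Section 1.2.1.2 reports efficacy data being available for 28 chronic-phase patients with T315I. The issue is the dose. Nor is Table 7-2 at fault for placing the fallback Sanger sample at switch Week 1 Day 1. The Amendment 1 protocol takes its Week 1 Day 1 sample before dosing, and moving the draw would achieve nothing unless the result were awaited.

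**Conclusion.** The concern holds for the Amendment 3 protocol summary. Its switch criterion admits T315I emerging on bosutinib and mutations against asciminib, no preventing condition offsets this, and the result conflicts with the dose statements in Sections 1.2.1.2 and 2.3. The conflict with Section 7.1.6 assumes that the rule recorded in the Amendment 2 log is still in force.

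The documents do not support the wider claim that the protocol as a whole lacks a T315I bar, since Section 7.1.2.2 and the current Section 7.1.6 could not be read. If Section 7.1.2.2 already bars T315I, only the summary needs correcting. Nor do they support any claim of bias in the primary or key secondary comparison.

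The size is unknown and probably small, bounded above by 74 patients. The correction is worth making because it is cheap and concerns which patients receive which dose. Confidence is moderate, given the unread sections.

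**What to change.** Make these changes in the protocol summary, and in Section 7.1.2.2 if it reads the same:

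1. Limit the mutation criterion to new BCR-ABL1 mutations that may cause resistance to bosutinib.
2. Add to the conditions preventing the switch: T315I known at the time of switch, or a known asciminib-resistance mutation. The bar should apply whichever of the seven criteria the patient meets.
3. State in Section 7.1.6 how V299L emerging on bosutinib is handled for the switch, since the logged rule names it but the asciminib dose rationale does not.

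No change to Table 7-2 is needed. The cost is a few lines of text, with no added visit, sample or assay. The real downside is that a few patients with T315I lose the switch when they have few options left. If the sponsor prefers to treat them, the protocol should say so, justify 40 mg BID for T315I and amend Section 7.1.6 to match.
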